10.8. Appendix 8: Abbreviations

Abbreviation	Term
AD	atopic dermatitis
AE	adverse event
ALT	alanine aminotransferase
ANOVA	analysis of variance
ANCOVA	analysis of covariate
AST	aspartate aminotransferase
BID	twice daily
BSA	body surface area
BUN	blood urea nitrogen
CAT	COPD assessment test
CFR	code of federal regulations
CHF	chronic heart failure
CI	confidence interval
CIG	Central Investigator Group
CIOMS	Council for International Organizations of Medical Sciences
CK	creatine kinase
CKD	chronic kidney disease
CO ₂	carbon dioxide
CONSORT	Consolidated Standards of Reporting Trials
COPD	chronic obstructive pulmonary disease
COVID-19	Coronavirus Disease (2019)
CPAP	continuous positive airway pressure
CRF	case report form
CRO	contract research organization
CRU	clinical research unit
CSR	clinical study report
CT	clinical trials
CTTI	clinical trials transformation initiative
DILI	drug-induced liver injury
CCI	
DMC	Data monitoring committee
DVT	deep vein thrombosis
ECG	electrocardiogram
EDC	electronic data capture
eCRF	electronic case report form
EC ₅₀	half maximal effective concentration
EDP	exposure during pregnancy
eGFR	Estimated glomerular filtration rate
EMA	European Medicines Agency
EOT	End of Treatment
CCI	
CCI	

Abbreviation	Term
EU	European Union
EudraCT	European Clinical Trials Database
FAS	Full Analysis Set
FDA	Food and Drug Administration
FSH	follicle-stimulating hormone
FTU	fingertip unit
GCP	Good Clinical Practice
GFR	glomerular filtration rate
GGT	Gamma-glutamyl transferase
GOLD	Global Initiative for Obstructive Lung Disease
HCP	Health Care Provider
HIPAA	Health Insurance Portability and Accountability Act
HRT	hormone replacement therapy
HVP	Home Visit Practitioner
IA	Interim Analysis
IB	Investigator's Brochure
ICF	Informed consent form
ICH	International Conference on Harmonisation
IC ₅₀	half maximal inhibitory concentration
ID	identification
IEC	Independent Ethics Committee
IL	interleukin
IMP	Investigational medicinal product
IND	investigational new drug application
INF- γ	Interferon gamma
INR	international normalized ratio
IP	investigational product
IRB	institutional review board
IRC	Internal Review Committee
IRT	interactive response technology
ISGA	Investigator's Static Global Assessment
IVC	Inferior vena cava
JAK	Janus kinase
LFT	liver function test
LSM	least squares mean
MAR	Missing Data Are Assumed
mMRC	British Medical Research Council
MMF	mycophenolate mofetil
MMP	matrix metalloproteinases
MMRM	mixed model for repeated measures
MMSE-2	Mini Mental State Examination
N/A	Not applicable
NIMP	Non-investigational medicinal product

Abbreviation	Term
NSAIDS	nonsteroidal anti-inflammatory drugs
NYHA	New York Heart Association
MR-NR	missing response as non-response
CCI	[REDACTED]
PCD	primary completion date
PDE-4	phosphodiesterase 4
CCI	[REDACTED]
PI	principal investigator
PK	Pharmacokinetic(s)
PRN	as needed
PRO	patient reported outcome
PACL	Protocol Administrative Change Letter
PT	prothrombin time
QC	quality control
QTcF	Fridericia's Correction Formula
RBC	red blood cell
RTC	Remote Trial Coordinator
SAE	serious adverse event
SAF	Safety Analysis Set
SD	stasis dermatitis
SoA	schedule of activities
SAP	Statistical Analysis Plan
SOP	standard operating procedure
SRSD	single reference safety document
SubI	sub investigator
SUSAR	suspected unexpected serious adverse reactions
TBili	total bilirubin
TCI	topical calcineurin inhibitor
TCS	topical corticosteroid
TGF β 1	transforming growth factor β 1
TIMP	tissue inhibitors of metalloproteinases
TNF α	tumor necrosis factor alpha
TSS	total sign score
% BSA	percent body surface area
ULN	upper limit of normal
US	United States
USA	United States of America
CCI	[REDACTED]
VHTN	venous hypertension
VI	venous insufficiency
VRCT	virtual randomized clinical trials
WBC	White blood cells

Abbreviation	Term
WOCBP	women of child-bearing potential

1. VERSION HISTORY

This statistical analysis plan (SAP) for Study C3291038 is based on Protocol Amendment 2 dated 19July2021.

Table 1. Summary of Changes

Version/Date	Associated Protocol Amendment	Rationale	Specific Changes
1 10Mar2020	Amendment 1 10January2020	N/A	N/A
2 11Mar2021	Amendment 1 10January2020	No efficacy data are collected after intercurrent event (ie, discontinuation of study intervention)	Estimand 3 and related analyses were removed
		Only one post-baseline assessment will be performed for these endpoints. All participant with post-baseline assessments can be included in analysis based on new visit windows.	New visit windows are defined for TSS, ISGA, %BSA in-person assessment, CCI
		Subset analyses will be performed just for in-person assessment endpoints.	“based on HVP in-person assessment” was added to Section 6.4 Subset Analyses
		Validation analysis will be described in a separate analysis plan	Validation Section was removed.
		Don’t need summary and listing for vital signs, height, weight and ECG	Vital signs and ECG were removed from Section 6
3 28Jul2021	Amendment 2 19Jul2021	For non-longitudinal endpoints, the assessments at EOT for early terminated participants are included in the analysis.	Estimand 1 was changed as a while-on-treatment estimand. Estimand 3 was added as a hypothetical estimand for longitudinal continuous endpoints
		Interim analysis may be performed	Details for interim analysis was added.

		To reduce sample size	Sample size was reduced to 70, significance level was changed to 5% one-sided. CI was changed to 90%
		For consistency with protocol	Screened population was added. Enrolled population was changed.
		Subgroup analysis will be performed by type of standard of care/skin type. This supportive analysis is not necessary.	Removed supportive analysis for TSS change from baseline at Week 6/EOT based on in-person assessment (ANCOVA model including type of standard of care/skin type)
4 16Sep2021	Amendment 2 19Jul2021	Sensitivity analyses	Added analyses for % change from baseline in TSS at Week 6 based on in-person assessment for observed cases and multiple imputation for missing data.
		Exclude the assessments far away from last dose	For Week 6 or EOT, the visit window cut at the last dose + 10 days.

2. INTRODUCTION

This SAP provides the detailed methodology for summary and statistical analyses of the data collected in Study C3291038. The summaries and analyses described in this SAP will be reported in the clinical study report (CSR). Validation analysis for comparison between in-person assessment and Central Readers assessments based on images will be described in a separate analysis plan and reported separately from the CSR.

This document may modify the plans outlined in the protocol; however, any major modifications of the primary endpoint definition or its analysis will also be reflected in a protocol amendment.

2.1. Study Objectives, Endpoints, and Estimands

2.1.1. Study Objectives and Endpoints

Study objectives and corresponding endpoints are provided in the Table 2 below.

Table 2. Study Objectives and Endpoints

Objectives	Endpoints
Primary	

 To evaluate the efficacy of crisaborole ointment, 2%, twice daily (BID) versus vehicle at Week 6 in participants with stasis dermatitis (SD) without active skin ulceration. 	
 Percent change from baseline in Total Sign Score (TSS) at Week 6/EOT (Home Visit Practitioner [HVP] in-person assessment).
Secondary Efficacy	
 Achievement of an Investigator's Static Global Assessment (ISGA) score of Clear (0) or Almost Clear (1) with at least a 2-grade improvement from baseline at all time points (analyze both HVP in-person assessment and Central Readers digital images assessment); Achievement of an ISGA score of Clear (0) or Almost Clear (1) at all time points (analyze both HVP in-person assessment and Central Readers digital images assessment); Percent change from baseline in TSS at all time points (Central Readers digital images assessment); Percent change from baseline in lesional % Body Surface Area (%BSA) at all time points (analyze both HVP in-person assessment and Central Readers digital images assessment).
Secondary Safety	

 To evaluate the safety and local tolerability of crisaborole ointment, 2%, BID versus vehicle in participants with SD without active skin ulceration. 	
 Incidence and severity of treatment emergent adverse events (AEs), including local tolerability events.
CCI	

2.1.2. Estimands

Only discontinuation of study intervention will be considered as an intercurrent event.

Estimand 1: The primary estimand of this study is a while-on-treatment estimand, which estimates the treatment effect of crisaborole compared with vehicle at Week 6/EOT. It includes the following 5 attributes:

- Population: participants ≥ 45 years of age with SD without active skin ulceration;
- Variable: non-longitudinal endpoints at Week 6/EOT;
- Treatment condition: crisaborole 2% BID or vehicle;
- Intercurrent event: all data after an intercurrent event of discontinuation of study intervention will be excluded, data at Week 6 or EOT (within date of last dose + 10 days) will be included;
- Population-level summary: difference in LSM for continuous endpoint and difference in proportion of participants with response for binary endpoints at Week 6/EOT between crisaborole ointment, 2%, BID and vehicle.

Estimand 1 will be used in analyzing the primary endpoint and it will also be used to analyze non-longitudinal continuous secondary endpoints %BSA in-person assessment CCI

CCI and non-longitudinal binary endpoints ISGA success (ISGA score of clear/almost clear with at least a 2-grade improvement from baseline) and ISGA clear/almost clear based on in-person assessment.

Estimand 2: The second estimand of this study is a composite estimand, which estimates the treatment effect of crisaborole compared with vehicle at each timepoint. It includes the following 4 attributes:

- Population: participants ≥ 45 years of age with SD without active skin ulceration;
- Variable: binary response endpoint per photography assessment, eg, response defined as a participant with an ISGA score of clear or almost clear with at least a 2-grade improvement from baseline at each time point; a participant after an intercurrent event of discontinuation of study intervention will be considered a non-responder for the visit of interest;
- Treatment condition: crisaborole 2% BID or vehicle;
- Intercurrent event: there will be no intercurrent event since the discontinuation of study intervention is part of the variable definition;
- Population-level summary: difference in proportion of participants with response at each time point between crisaborole ointment, 2%, BID and vehicle.

Estimand 2 will be used in analyzing all applicable longitudinal secondary binary endpoints.

Estimand 3: The third estimand of this study is a hypothetical estimand, which estimates the treatment effect of crisaborole compared with vehicle at each time point under the scenario of no discontinuation of study intervention. It includes the following 5 attributes:

- Population: participants ≥ 45 years of age with SD without active skin ulceration;
- Variable: percent change from baseline in TSS at each time point;
- Treatment condition: crisaborole 2% BID or vehicle;
- Intercurrent event: all data collected after any intercurrent events will be excluded;
- Population-level summary: difference in mean percent change from baseline in TSS at each time point between crisaborole ointment, 2%, BID and vehicle.

Estimand 3 will be used in analyzing the longitudinal continuous endpoints.

2.2. Study Design

Study C3291038 is a Phase 2a, randomized, double-blind, vehicle-controlled, parallel-group, proof-of-concept study to evaluate the efficacy, safety, and local tolerability of 6 weeks of treatment with crisaborole in adult participants with SD without active skin ulceration.

Approximately 70 eligible participants will be randomized into the double-blind treatment period in a 1:1 ratio to receive crisaborole ointment, 2% or vehicle twice daily for 6 weeks.

[figure not shown]
The study will recruit male and female participants aged ≥ 45 years with a clinical diagnosis of SD. Participants who meet all inclusion but none of the exclusion criteria presented in Section 5 of the protocol will be eligible to participate in the study. If a participant meets any of the exclusion criteria, the participant will be excluded.

The total duration of participation in the study will be up to 14 weeks, including up to 4 weeks for screening, a 6-week double-blind treatment period, and a follow-up period of 4 weeks after treatment completion.

Study enrollment and management will be de-centralized, where participants do not visit an investigator or a clinic for clinical assessment. The participants will participate in the study at home. The sponsor (or designee) will provide home visits by qualified HVP, remote contact by telemedicine (or telephone), and clinical database electronic case report forms (eCRFs), eDiary, and other electronic data entries from 3rd party vendors for study data collection.

Participants who withdraw from further study intervention treatment (but do not withdraw consent for further data gathering) should continue to complete all scheduled assessments at the EOT visit and complete the follow-up phase of the study.

Figure 1. Schema

3. ENDPOINTS AND BASELINE VARIABLES: DEFINITIONS AND CONVENTIONS

TSS, ISGA and lesional %BSA will be assessed in-person by HVP at the home visits at screening, baseline, and Week 6 (or early termination) and will be used for the primary analyses. These efficacy parameters will also be remotely assessed at all scheduled timepoints by an expert dermatologist central reader reviewing digital imaging of the lower extremities acquired by the participant. The data based on Central Readers assessments will be used for supportive analyses. Only initial Central Readers assessments will be used for supportive analyses. Central Readers re-assessments will be used for validation and reliability analyses.

3.1. Primary Endpoint

The primary efficacy endpoint is a percent change from baseline in TSS at Week 6/EOT (HVP in-person assessment).

3.2. Secondary Endpoints

The secondary endpoints are:

- Achievement of an ISGA score of Clear (0) or Almost Clear (1) with at least a 2-grade improvement from baseline at all time points (analyze both HVP in-person assessment and Central Readers digital images assessment).
- Achievement of an ISGA score of Clear (0) or Almost Clear (1) at all time points (analyze both HVP in-person assessment and Central Readers digital images assessment).
- Percent change from baseline in TSS at all time points (Central Readers digital images assessment).
- Percent change from baseline in lesional %BSA at all time points (analyze both HVP in-person assessment and Central Readers digital images assessment).

CCI

3.4. Baseline Variables

Demographic and baseline characteristics include:

- Age
- Sex
- Race
- Ethnicity
- Height (cm)
- Weight (kg)
- Body mass index (kg/m²)
- Duration of disease (years)
- Prior TCS/TCI
- Fitzpatrick Skin Type
- Type of standard of care
- TSS
- ISGA
- %BSA

The baseline value is defined as the last observation up to and including Day 1 of intervention period. For daily assessed endpoints, the average of 7-day scores immediately prior to Day 1 (Day -6 to Day 1) will be used as the baseline.

3.5. Safety Endpoints

Safety will be assessed by medical history, physical examinations, vital signs, electrocardiograms (ECG), clinical laboratory tests, and the spontaneous reporting of AEs, in all participants who received at least one dose of study intervention. Unscheduled safety assessments may be performed at any time during the study to assess any perceived safety concerns. Investigators and Pfizer Clinicians will review individual participant data throughout the conduct of the study to ensure participants' well-being.

3.5.1. Adverse Events

An AE is considered treatment-emergent adverse event (TEAE) to a given treatment if the event start date is on or after the treatment period start date and before end of study.

Safety endpoints will be assessed by the spontaneous reporting of:

- Incidence of TEAEs
- Incidence of serious adverse events (SAEs)
- Incidence of AEs leading to discontinuation

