
To evaluate the safety and local tolerability of crisaborole ointment, 2%, BID versus vehicle in participants with SD without active skin ulceration.	
Incidence and severity of treatment emergent adverse events, including local tolerability events.
Estimands	
Only discontinuation of study intervention will be considered as an intercurrent event.	
The primary estimand of this study is a while-on-treatment estimand, which estimates the treatment effect of crisaborole compared with vehicle at Week 6 or EOT. It includes the following 5 attributes:	

Population: Participants \geq45 years of age with SD without active skin ulceration;Variable: non-longitudinal endpoints at Week 6/EOT;Treatment condition: crisaborole 2% BID or vehicle;Intercurrent event: all data after an intercurrent event of discontinuation of study intervention will be excluded, data at Week 6/EOT will be included;Population-level summary: difference in LSM for continuous endpoints and difference in proportion of participants with response for binary endpoints at Week 6/EOT between crisaborole ointment, 2%, BID versus vehicle.	
See Section 9.1.1 for additional information on estimands.	

Overall Design:

This is a Phase 2a, randomized, double-blind, vehicle-controlled, parallel-group, proof-of-concept study enrolling approximately 70 eligible participants randomized into the double-blind treatment period in a 1:1 ratio to receive BID crisaborole ointment 2% or vehicle for 43 days.

The total duration of participation in the study is up to 14 weeks, including up to 4 weeks for screening, a 6-week double-blind treatment period, and follow-up period of 4 weeks after treatment completion.

Disclosure Statement:

This is a Parallel Treatment study with 2 Arms that is Sponsor, Investigator and Participant blinded.

Number of Participants:

Approximately 70 participants will be randomized.

Intervention Groups and Duration:

[figure not shown]
Group 1 (N=35): Crisaborole ointment, 2% (w/w) BID for 43 days

Group 2 (N=35): Vehicle BID for 43 days

Data Monitoring Committee:

An IRC will be utilized if an IA is performed

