3. OBJECTIVES, ESTIMANDS AND ENDPOINTS

Objectives	Endpoints
Primary	

To evaluate the efficacy of crisaborole ointment, 2%, BID versus vehicle at Week 6 in participants with stasis dermatitis without active skin ulceration.	
Percent change from baseline in Total Sign Score (TSS) at Week 6/EOT (in-person assessment).
Secondary Efficacy	

To evaluate the efficacy of crisaborole ointment, 2%, BID versus vehicle over time in	
Achievement of an Investigator's Static Global Assessment (ISGA) score of Clear (0) or Almost Clear (1) with at least a 2-grade

Objectives	Endpoints
participants with SD without active skin ulceration.	
improvement from baseline at all time points (analyze both in-person assessment and Central Readers digital images assessment);
 
• Achievement of an ISGA score of Clear (0) or Almost Clear (1) at all time points (analyze both in-person assessment and Central Readers digital images assessment);• Percent change from baseline in TSS at all time points (Central Readers digital images assessment);• Percent change from baseline in lesional % Body Surface Area (%BSA) at all time points (analyze both in-person assessment and Central Readers digital images assessment).
Secondary Safety	

• To evaluate the safety and local tolerability of crisaborole ointment, 2%, BID versus vehicle in participants with SD without active skin ulceration.	
• Incidence and severity of treatment emergent adverse events, including local tolerability events.
CCI	

CCI		
Estimands		

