8.3.1. Time Period and Frequency for Collecting AE and SAE Information

The time period for actively eliciting and collecting AEs and SAEs (“active collection period”) for each participant begins from the time the participant provides informed consent, which is obtained before the participant’s participation in the study (ie, before undergoing any study-related procedure and/or receiving study intervention), through and including a minimum of 28 calendar days after the last administration of the study intervention.

For participants who are screen failures, the active collection period ends when screen failure status is determined.

Follow up by the investigator continues throughout and after the active collection period and until the AE or SAE or its sequelae resolve or stabilize at a level acceptable to the investigator, and Pfizer concurs with that assessment.

If the participant withdraws from the study and also withdraws consent for the collection of future information, the active collection period ends when consent is withdrawn.

If a participant definitively discontinues or temporarily discontinues study intervention because of an AE or SAE, the AE or SAE must be recorded on the CRF and the SAE reported using the CT SAE Report Form.

Investigators are not obligated to actively seek AE or SAE after the participant has concluded study participation. However, if the investigator learns of any SAE, including a death, at any time after a participant has completed the study, and he/she considers the event to be reasonably related to the study intervention, the investigator must promptly report the SAE to Pfizer using the CT SAE Report Form.

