10.3.1. Definition of AE

AE Definition

• An AE is any untoward medical occurrence in a patient or clinical study participant, temporally associated with the use of study intervention, whether or not considered related to the study intervention.• NOTE: An AE can therefore be any unfavorable and unintended sign (including an abnormal laboratory finding), symptom, or disease (new or exacerbated) temporally associated with the use of study intervention.

Events Meeting the AE Definition

• Any abnormal laboratory test results (hematology, clinical chemistry, or urinalysis) or other safety assessments (eg, ECG, radiological scans, vital signs measurements), including those that worsen from baseline, considered clinically significant in the medical and scientific judgment of the investigator (ie, not related to progression of underlying disease).• Exacerbation of a chronic or intermittent pre-existing condition including either an increase in frequency and/or intensity of the condition.• New conditions detected or diagnosed after study intervention administration even though it may have been present before the start of the study.• Signs, symptoms, or the clinical sequelae of a suspected drug-drug interaction.• Signs, symptoms, or the clinical sequelae of a suspected overdose of either study intervention or a concomitant medication. Overdose per se will not be reported as an AE/SAE unless it is an intentional overdose taken with possible suicidal/self-harming intent. Such overdoses should be reported regardless of sequelae.• “Lack of efficacy” or “failure of expected pharmacological action” per se will not be reported as an AE or SAE. Such instances will be captured in the efficacy assessments. However, the signs, symptoms, and/or clinical sequelae resulting from lack of efficacy will be reported as AE or SAE if they fulfil the definition of an AE or SAE.

Events NOT Meeting the AE Definition

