- If the investigator does not know whether or not the study intervention caused the event, then the event will be handled as “related to study intervention” for reporting purposes, as defined by the sponsor" and "In addition, if the investigator determines that an SAE is associated with study procedures, the investigator must record this causal relationship in the source documents and CRF, and report such an

assessment in the dedicated section of the CT SAE Report Form and in accordance with the SAE reporting requirements.

Follow-up of AEs and SAEs

- The investigator is obligated to perform or arrange for the conduct of supplemental measurements and/or evaluations as medically indicated or as requested by Pfizer Safety to elucidate the nature and/or causality of the AE or SAE as fully as possible. This may include additional laboratory tests or investigations, histopathological examinations, or consultation with other health care professionals.
- If a participant dies during participation in the study or during a recognized follow-up period, the investigator will provide Pfizer Safety with a copy of any post-mortem findings including histopathology.
- New or updated information will be recorded in the originally completed CRF.
- The investigator will submit any updated SAE data to the sponsor within 24 hours of receipt of the information.

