6.6. Safety Summaries and Analyses

Safety analyses will be summarized in accordance with Pfizer Data Standards.

All clinical AEs, SAEs, TEAEs, withdrawal due to AEs, will be reviewed and summarized on an ongoing basis during the study to evaluate the safety of participants.

Safety data will be presented in tabular and/or graphical format and summarized descriptively, where appropriate. All safety endpoints will be listed and summarized in accordance with Pfizer Standards. Categorical outcomes (eg, AEs) will be summarized by participant counts and percentage. Continuous outcome (eg, pulse rate, etc) will be summarized using n, mean, median, standard deviation, etc. Participant listings will be produced for these safety endpoints accordingly.

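### The SAP defines a treatment-emergent adverse event by start date only, and neither document says how to record an adverse event from screening that worsens on treatment

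*SAP*

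**What the plan says.** SAP 3.5.1 makes an AE a treatment-emergent AE (TEAE) if "the event start date is on or after the treatment period start date and before end of study". Start date is the only criterion. Neither document adds a criterion based on worsening or increased severity.

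The definition feeds the secondary safety endpoint in Protocol 3, repeated in SAP Table 2: "Incidence and severity of treatment emergent adverse events, including local tolerability events".

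Active AE collection "begins from the time the participant provides informed consent" (Protocol 8.3.1), and the study period is described as "including up to 4 weeks for screening" (Protocol 1.1). The schedule of activities asks for AEs at every screening contact.

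Two parts of Protocol Appendix 3 bear on an event that changes over time:

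- Protocol 10.3.1 lists among events that meet the AE definition: "Exacerbation of a chronic or intermittent pre-existing condition including either an increase in frequency and/or intensity of the condition".
- Protocol 10.3.3, on follow-up, states: "New or updated information will be recorded in the originally completed CRF".

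For everything else, SAP 6.6 defers to sponsor standards that are not reproduced: "Safety analyses will be summarized in accordance with Pfizer Data Standards".

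**The concern.** An AE that begins after consent but before the first application has a pre-dose start date. If it becomes more intense under the ointment, the start-date rule cannot recognise the change unless the site opens a second record. The documents do not tell sites whether to do so.

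Two sites could therefore record the same clinical course differently, and only one version would produce a TEAE. Both parts of the endpoint are exposed: the participant may be absent from the incidence count, and the higher on-treatment grade may be absent from the severity table. The loss need not be equal between arms. If the active ointment caused more worsening than vehicle, more events would drop out of the active arm, and the comparison would look more favourable than it should.

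**Working it through.** There is no stated figure to reproduce. The check is mainly a comparison of texts, followed by an illustration of size.

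**Step 1. Can an AE have a pre-dose start date?** Yes. Collection starts at consent (Protocol 8.3.1), and screening lasts up to 4 weeks (Protocol 1.1).

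**Step 2. How is later worsening of that AE recorded?** Two routes can be read from the protocol:

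| Route | Basis | Start date in the data | TEAE under SAP 3.5.1? |
|---|---|---|---|
| New record dated at the worsening | Protocol 10.3.1: an exacerbation meets the AE definition | On treatment | Yes |
| Original record updated | Protocol 10.3.3: new information goes into the record first completed | In screening | No |

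That the updated record keeps its screening start date is an inference. Protocol 10.3.3 does not mention start dates or severity changes. It is the natural result of updating a record rather than opening one, and no text says otherwise.

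**Step 3. Does any text choose between the routes?** No such text appears in Protocol 8.3, 9.4.5 or Appendix 3, or in SAP 3.5.1, 6.6, 6.6.1 or Appendix 2.

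**Step 4. Who is affected?** An AE must meet all of these conditions: onset between consent and first application; still open at first application; not an expected sign of stasis dermatitis; more intense on treatment; and kept as one record.

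**Step 5. Size, by assumption only.** The documents give no rate p for such events. With n = 35 per arm (Protocol 9.2):

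- expected number per arm = n × p
- chance of at least one in an arm = 1 − (1 − p)^n

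| Assumed p | Expected per arm | Chance of at least one |
|---|---|---|
| 1% | 35 × 0.01 = 0.35 | 1 − 0.99^35 = 30% |
| 3% | 35 × 0.03 = 1.05 | 1 − 0.97^35 = 66% |
| 5% | 35 × 0.05 = 1.75 | 1 − 0.95^35 = 83% |
| 10% | 35 × 0.10 = 3.5 | 1 − 0.90^35 = 97% |

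Here p is the share of participants with a screening-onset AE that worsens on treatment. The number lost is at most this, because any event entered as a new record is counted. One participant in 35 is 1/35 = 2.9 percentage points of incidence.

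**The case against.** A reader might infer that events beginning in screening and worsening under the ointment are never counted. The documents do not support that. Protocol 10.3.1 makes an exacerbation an AE, and if it is entered with its own on-treatment start date, it meets the SAP rule.

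A reader might also take worsening lower-leg itch, pain or erythema as the typical lost event. That mostly fails. Protocol 2.2 describes these as features of stasis dermatitis itself, and Protocol 10.3.1 excludes expected signs and symptoms of the studied disease from AEs unless they are more severe than expected. Before dosing they would ordinarily be disease history, with no AE record open. If they worsen beyond expectation on treatment, the AE first arises then and counts. Likewise, a medical-history condition that worsens can be entered as a new AE.

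Further points on the other side:

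- The follow-up instruction in Protocol 10.3.3 is general. It does not order sites to merge a worsening into an old record. This stands: the defect is silence on the convention, not an instruction to hide worsening.
- SAP 3.5.1 also lists serious AEs and "Incidence of AEs leading to discontinuation" without limiting them to TEAEs, so a screening-onset event that became serious or stopped treatment could still appear there. This stands in part. The list in SAP 6.6.1 can be read as limiting the serious events to treatment-emergent ones. Neither list would catch a local reaction that goes from mild to severe but is not serious and does not lead to discontinuation.
- SAP 6.6 has all clinical AEs reviewed and summarised on an ongoing basis during the study. That gives some visibility, but it is not the TEAE endpoint.
- The sponsor's standards may cover worsening. Their content is not given, and they cannot be assumed to override an explicit SAP rule. If they include a worsening criterion, SAP 3.5.1 conflicts with them; if not, the gap remains.
- Safety analysis is descriptive (Protocol 9.4.5), and the rule is the same in both blinded arms. True, but an identical rule does not ensure equal loss if worsening differs by arm.

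**Conclusion.** The point holds as a gap in definition and recording. The TEAE rule is start-date only, the protocol can be read as supporting two recording routes for a screening AE that worsens on treatment, and nothing chooses between them. On one route the worsening is counted; on the other it is missing from both incidence and severity of TEAEs.

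The size cannot be computed from the documents. The range of about 0.35 to 3.5 participants per arm of 35 rests wholly on an assumed rate of 1% to 10% and is an upper limit at each assumed rate, since some of these events would be entered as new records. The primary efficacy analysis is untouched. The gap should still be closed, because it affects a named secondary endpoint, the remedy is cheap, and counts should not depend on a site's recording habit.

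**What to change.** Either of two changes would do.

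1. **Preferred: extend the definition in SAP 3.5.1.** A TEAE is an AE that starts on or after the first application, or that starts earlier and increases in severity or becomes serious on or after the first application. Take severity for the TEAE tables as the maximum after first application.
2. **Alternative: fix the recording convention.** Require a new AE record, dated at the worsening, whenever an AE opened in screening increases in severity on treatment, and reconcile Protocol 10.3.1 and 10.3.3 accordingly.

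The SAP change is one sentence. The operational cost is that sites must record severity changes with dates, which may need a change to the case report form or site instructions. TEAE counts may rise slightly.
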